9.2 Determination of Sample Size

Assuming a 2-sided test with $\alpha = 0.05$, a common standard deviation (SD) of 3.5 mmHg at each time point yielding a common SD of 3.0 for the diurnal mean, and a correlation among time points of 0.60, 49 ITT subjects per arm yields at least 90% power to demonstrate superiority of netarsudil (0.01%, 0.02% or 0.04%) to placebo in mean diurnal study eye IOP (average of 09:00, 11:00, and 16:00 hours) at the Week 4 visit assuming a difference of at least 2.0 mmHg in the mean diurnal IOP. The study will be considered a success and superiority of netarsudil to placebo will be concluded if the two-sided p-value ≤ 0.05 at Week 4. Accounting for approximately a 5% discontinuation rate, 52 subjects per arm (208 total) will be enrolled.

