Mean percent change from baseline in mean diurnal IOP and mean percent change from diurnally adjusted baseline IOP at each time point will be analyzed using two-sample t-tests, between netarsudil (0.01%, 0.02% or 0.04%) and placebo, at each time point and visit, including two-sample t-tests and 95% t-distribution confidence intervals on the difference (netarsudil - placebo).

Mean diurnal IOP values will be constructed by averaging the 3 diurnal IOP measurements on each of Week 1, Week 2, and Week 4 visits. Mean diurnal baseline IOP will be constructed as the average of the three Day 1 IOP measurements. Mean change from mean baseline diurnal IOP will be created by taking the average of the 3 time points on each of Week 1, Week 2, and Week 4 visits and subtracting the single mean baseline diurnal IOP measurement.

Sub-group analyses based upon pre-study characteristics such as site, demographics, baseline IOP categories, or pre-study ocular hypotensive medications may be completed to further investigate the efficacy measures.

Analyses of IOP will also include summarizing the number and percentage of study eyes achieving mean diurnal IOP reduction from baseline of ≥ 4 to ≥ 12 mmHg in 2 mmHg increments and percent reduction from baseline of $\geq 5\%$ to $\geq 40\%$ in 5% increments at Week 1, Week 2, and Week 4. Additionally, the number and percentage of study eyes attaining a mean diurnal IOP of ≤ 22 to ≤ 14 mmHg in 1 mmHg increments will be summarized at Week 1, Week 2, and Week 4. Fisher's exact test (2-sided p-values) will be used to test differences between netarsudil (0.01, 0.02% or 0.04%) versus placebo for each category at each visit. These analyses will be presented for both the ITT and PP populations with observed data only.

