Appendix 6 Sample SAS Code

The following SAS code will be used for multiple imputations using the Monte-Carlo Markov Chain method, where a separate model will be fit for each time point at each visit.

```
proc mi data = indata seed = 6876 out = outdata1;  
  
mcmc initial = em;  
  
var trt01pn baseline IOP;  
  
run;
```

where

- *indata* is the name of the input dataset
- *outdata1* is the name of the output dataset
- *trt01pn* is the name of the treatment group variable in numeric format
- *baseline* captures the baseline IOP for the given time point
- *IOP* is the name of the IOP measure.

Thirty complete data sets will be generated from the above code. Each complete data set will be used to analyze this primary efficacy endpoint separately using analysis of variance. Then, the SAS procedure MIANALYZE will be used to analyze the results from the 30 complete data sets to generate a combined inference. The following SAS code will be used:

```
ods output diffs = outdata2;  
  
proc mixed data= outdata1;  
  
by _IMPUTATION_;  
  
class trt01pn;  
  
model IOP = trt01pn baseline;  
  
lsmeans trt01pn / cl pdiff;  
  
run;  
  
proc sort data= outdata2;  
  
by trt01pn _trt01pn;
```

```
run;  
  
ods output ParameterEstimates = outdata3;  
  
proc mianalyze data= outdata2 alpha = 0.05;  
    by trt01pn _trt01pn;  
    class trt01pn _trt01pn;  
    modeleffects estimate;  
    stderr;
```

run;

where

- *outdata1* is the name of the input dataset from Proc MI
- *_IMPUTATION_* is the imputation number
- *trt01pn* is the name of the treatment group variable in numeric format
- *IOP* is the name of the IOP measure
- *baseline* captures the baseline IOP for the given time point
- *outdata2* is the name of the output dataset that contains the statistical results of the difference between treatment groups
- *outdata3* is the name of the output dataset that contains summary and inferential statistics.

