4.2 Masking

Treatment assignments will be masked to the Investigator, the clinical study team (Sponsor, personnel involved in day to day study management, Monitors, Data Managers, and Statisticians), and the subjects for the duration of the study. Only in case of medical emergency or occurrence of AEs that warrant unmasking in the opinion of the Investigator, will the treatment assignment(s) be unmasked and made available to the Investigator and the Sponsor Medical Monitor or designee. Individual unmasking by the Investigator will normally result in withdrawal of the subject from the study and should only be performed for the specific subject requiring unmasking. In the absence of medical need, the randomization code will not be available to the above personnel until after the study is completed and the database is unlocked.

5. Sample Size and Power Considerations

Assuming a two-sided test with alpha = 0.05, a common standard deviation (SD) of 3.5 mmHg at each time point yielding a common SD of 3.0 for the diurnal mean, and a correlation among time points of 0.60, 49 intent-to-treat (ITT) subjects per arm yields at least 90% power to demonstrate superiority of netarsudil (0.01%, 0.02%, or 0.04%) to placebo in mean diurnal study eye IOP (average of 09:00, 11:00, and 16:00 hours) at the Week 4 visit assuming a difference of at least 2.0 mmHg in the mean diurnal IOP. Accounting for approximately a 5% discontinuation rate, 52 subjects per arm (208 total) will be enrolled.

6. Data Preparation

Study data will be recorded via electronic case report forms (eCRF). Each authorized study staff member will receive a unique access account in order to use the Electronic Data Capture (EDC) system. Access accounts will not be shared among study staff. Authorized users will make entries and/or changes to the eCRFs via a secure internet access. Each completed set of eCRFs will be reviewed by the Investigator

who will then electronically sign and date the eCRF confirming that data for the subjects are complete and accurate.

Final analyses outlined in this document will be carried out after the following have occurred:

- All data management requirements are met according to [REDACTED] standard operating procedures, including data entry, performance of edit and validation checks, documentation and resolution of data queries, and database lock with written authorization provided by appropriate [REDACTED] and Sponsor personnel.

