13.1 Primary Efficacy Analysis

The primary efficacy endpoint will be the mean of mean diurnal IOP at Week 4 (Day 29). The primary analysis of the primary endpoint will employ an analysis of covariance (ANCOVA) model with mean of mean diurnal IOP at Week 4 as the response, baseline mean of mean diurnal IOP as a covariate, and treatment as a main effect, using the ITT population with MCMC multiple imputation techniques used to impute missing data. The least squares (LS) mean differences (netarsudil – placebo) will be presented separately for netarsudil 0.01%, 0.02%, and 0.04% as well as two-sided p-values and 95% CIs. For a given comparison, if the p-value is <0.05 and the point estimate of the LS mean difference is < 0, then the netarsudil group will be considered superior to the placebo.

The following SAS code will be used for multiple imputations using the MCMC method:

```
proc mi data = inidata seed = 48669 out = outdata1;
  mcmc initial = em;
  var trt01pn baseline IOP;
  run;
  where
    - inidata is the name of the input dataset
    - outdata is the name of the output dataset
    - trt01pn is the name of the treatment group variable in numeric format
    - baseline is the corresponding baseline IOP for a given time point
    - IOP is the name of the IOP measure.
```

Five (5) complete data sets will be generated from the above code. Each complete data set will be used to analyze this primary efficacy endpoint separately using ANCOVA. Then, the SAS procedure MIANALYZE will be used to analyze the results from the 5 complete data sets to generate a combined inference. The following SAS code will be used:

```
ods output diffs = outdata2;
proc mixed data = outdata1;
  class trt01pn;
  model IOP = trt01pn baseline;
  lsmeans trt01pn / cl pdiff;
```

```

by _Imputation_;
run;

proc sort data = outdata2;
  by trt01pn trt01pn;
run;

ods output ParameterEstimates = outdata3;

proc mianalyze data = outdata2 alpha = 0.05;
  by trt01pn trt01pn;
  modeleffects estimate;
  stderr stderr;
run;

```

where

- *IOP* is the name of the IOP measure
- *trt01pn* is the name of the treatment group variable in numeric format
- *outdata2* is the name of the output dataset that contains the statistical results of the differences between treatment groups
- *outdata3* is the name of the output dataset that contains summary and inferential statistics.

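### The plan points to imputing each Week 4 clock time on its own and does not say when the diurnal mean is formed; averaging separately imputed readings drops their within-visit correlation and misstates the primary standard error.

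*Protocol*

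**What the plan says.** The primary response is the Week 4 diurnal mean, analysed by ANCOVA in the ITT population after MCMC multiple imputation (Protocol 9.5.2, SAP 13.1). Protocol 9.6.2 explains how the response is built: "Mean diurnal IOP values will be constructed by averaging the 3 diurnal IOP measurements". The sample-size text (Protocol 9.2, repeated in SAP section 5) assumes "a correlation among time points of 0.60" and "a common standard deviation (SD) of 3.5 mmHg at each time point yielding a common SD of 3.0 for the diurnal mean".

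On imputation, Protocol Appendix 6 says "a separate model will be fit for each time point at each visit". The PROC MI variable list has three entries: treatment, one baseline and one IOP.

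SAP section 1 makes the SAP's methods replace the protocol's. SAP 13.1 keeps the three-entry list and describes the baseline variable this way: it "is the corresponding baseline IOP for a given time point". It omits the sentence about separate models and contains no step that forms the diurnal mean. SAP section 18 declares one departure from the protocol, the change of the significance rule from ≤0.05 to <0.05. It mentions no change in the unit of imputation.

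**The concern.** A subject who misses the whole Week 4 visit needs three imputed readings. If each comes from its own model, no model contains two clock times, so nothing carries the within-visit residual correlation into the imputed values. The average of three readings with independent residuals varies less than a real diurnal mean. The completed data then look too homogeneous, and the spread between imputations is also too small. Rubin's rules combine these two quantities, so the standard error, confidence interval and p-value are affected for all three primary contrasts.

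A related loss arises with partial visits. Early discontinuation calls for Visit 6.0 procedures, which is the 09:00 visit (Protocol Appendix 1). If such an exit falls in the Week 4 window, separate models ignore the observed 09:00 reading when filling in 11:00 and 16:00.

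Analyses of a single clock time do not have this problem. It arises only when separately imputed readings are averaged.

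**Working it through.** **Inputs from the documents.** SD 3.5 per clock time, correlation 0.60, difference 2.0 mmHg, two-sided 0.05, 49 evaluable and 52 enrolled per arm, about 5% discontinuation (Protocol 9.2). Five imputations (SAP 13.1); 30 in Protocol Appendix 6.

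**Assumption.** The documents give no baseline-to-Week 4 correlation c. Values of 0, 0.3 and 0.5 were tried.

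**1. The plan's own figures reproduce.** SD of the mean = 3.5 × √((1 + 2 × 0.60)/3) = 2.997. Noncentral-t power is 0.898 at 48 per arm and 0.904 at 49. 49/0.95 = 51.6, so 52.

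**2. What separate imputation removes.** With residual correlation r, the mean of three readings has residual variance σ²(1 + 2r)/3. With independent draws it is σ²/3. The ratio is k = 1/(1 + 2r).
- r = 0.60 (baseline explains nothing): k = 1/2.2 = 0.455.
- If every baseline reading correlates c with every Week 4 reading, r given the matched baseline is (0.60 − 1.4c²)/(1 − c²). At c = 0.5 this is 0.25/0.75 = 0.33, so r = 0.3 (k = 1/1.6 = 0.625) is a fair low case.

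**3. Rubin variance for an arm mean**, in units of σ²/n (σ² being the variance of the diurnal mean), with missing fraction p and m = 5:
- within: U = (1 − p) + pk
- between: B = pk/(1 − p)
- reported: T = U + 1.2B
- actual: 1/(1 − p) + B/5

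At p = 0.05 and k = 0.455: U = 0.973, B = 0.0239, T = 1.001, actual = 1.057. The SE ratio is √(1.001/1.057) = 0.973. The level is 2[1 − Φ(1.96 × 0.973)], about 5.7%.

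The same formula gives 0.947 (6.3%) at p = 0.10 and 0.913 (7.4%) at p = 0.17. With k = 0.625 and p = 0.05 it gives 0.982 (5.4%).

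**4. Simulation under the null.** Four arms of 52, whole Week 4 visit missing at random, ANCOVA on mean baseline, Rubin's rules, independent draws:

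| Missing | Method | Reported SE ÷ true SD | Two-sided level |
|---|---|---|---|
| 3 of 52, all arms | separate, then average | 0.96–0.99 | 5.5–6.0% |
| 3 of 52, all arms | joint, then average | 0.99–1.02 | 4.8–5.2% |
| 3 of 52, all arms | diurnal mean imputed directly | 0.99–1.02 | 4.8–5.3% |
| 5 of 52, all arms | separate, then average | 0.94–0.98 | 5.5–6.6% |
| 9 of 52, active arms only | separate, then average | about 0.95 | about 6.3% |
| 9 of 52, all arms | separate, then average | about 0.90–0.91 | 7.2–7.6% |

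Thirty imputations instead of five leave the ratio at 0.96–0.97 with 3 of 52 missing, so the number of imputations is not the cause.

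**5. Plain reading.** With 3 of 52 missing and c = 0, the separate-model SE averages 0.589. Complete data on 52 per arm would give 3.0 × √(2/52) = 0.588; the 49 observed give 3.0 × √(2/49) = 0.606. The missing visits are treated as costing almost no precision.

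**6. If a reused seed reproduces the draws.** The three residuals then coincide and k = 3/2.2 = 1.364. At p = 0.05: U = 1.018, B = 0.0718, T = 1.104, actual = 1.067, ratio 1.017. Simulation gave 1.01–1.04 with 3 of 52 missing (level 4.2–4.7%) and 1.05–1.16 with 10 of 52.

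**The case against.** **The explicit sentence is not in the governing document.** It stands in the protocol text supplied, Amendment 1. The SAP is written for Amendment 2, claims precedence and omits it. The SAP code passes PROC MI output straight to the ANCOVA and says each completed data set analyses the primary endpoint, so the imputed variable could be the diurnal mean itself. On that reading the error disappears. This stands as a possible reading, but the SAP does not settle it. Its baseline is defined for a clock time, its output list needs imputed values at each clock time (Table 14.2.1.1.3, Figure 14.2.7), and section 18 declares no change from Appendix 6.

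**The direction is not fixed.** A reader might infer that the reported standard error must be too small. Both documents print a single seed. If it is reused for each clock time with the same subjects missing, and the software repeats its random stream (an assumption), the error is conservative. This stands.

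**The draws are not unrelated.** A reader might infer that the imputed diurnal mean has SD 3.5/√3 = 2.02 instead of 3.0. That holds only if baseline explains nothing. The three values share the arm and use time-matched baselines, and only the residual correlation is lost.

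**The missing fraction may be modest.** A reader might take the 16.7% cornea verticillata incidence with once-daily dosing (Protocol 1.1) as the Week 4 missing fraction. First detection there was at 2–13 weeks, and subjects detected at Visit 6 can still have Week 4 readings. Stopping on any verticillata (Protocol 3.1) and the ±3-day Week 4 window (SAP 8.5) could push missingness above 5%, but 17% in every arm is an upper scenario, not a forecast.

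**Other safeguards exist.** Observed-data ANCOVA and an unstructured MMRM are prespecified and do not use this imputation. They help interpretation but do not correct the primary p-value. At 5% missing the excess is roughly 0.5 to 1 percentage point, in a Phase 2 study that makes three unadjusted comparisons.

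**Conclusion.** The point holds conditionally. If the Appendix 6 rule is followed and the three imputed Week 4 readings are then averaged, the imputation contradicts the correlation on which the plan's own sample size rests.

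With independent draws the primary standard error is about 1–4% too small at the planned 5% missing (level about 5.5–6%). It is about 5% too small with roughly 17% missing in active arms only (about 6.3%), and about 9% too small in the upper scenario of 17% in all arms (about 7.2–7.6%). With reproduced draws the error is conservative, and small at the planned missingness. With the diurnal mean imputed directly there is no such error.

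These sizes assume whole-visit missingness at random, the planned SD and correlation, and the stated range for the baseline correlation. The documents do not establish that the standard error will be too small. They leave its accuracy to a programming choice that the SAP should make. The effect is modest, but the choice should be settled because it concerns all three primary contrasts.

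**What to change.** In SAP 13.1, choose one of these and write it down:

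- **Joint imputation.** Use one row per subject and one imputation model containing treatment (as indicator variables, or run by arm), the three baseline readings and the three Week 4 readings. Average the three readings within each completed data set, then fit the ANCOVA. Treatment must stay in the model; a list of the six readings alone would pull the contrasts toward zero.
- **Direct imputation.** State that, for the primary analysis, the imputed variable is the Week 4 diurnal mean and the baseline variable is the mean diurnal baseline. This is simpler, but it does not use the observed readings of a partly completed visit.

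Apply the same choice to Weeks 1 and 2. List the change from Protocol Appendix 6 in SAP section 18, together with the move from 30 to 5 imputations, which is also undeclared there.

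The cost is a few lines of code and wording. Compared with separate models and independent draws, reported standard errors become slightly larger. The sample size stays at 49 evaluable and 52 enrolled per arm.

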The purpose of this statistical analysis plan (SAP) is to describe the planned analyses and reporting for protocol AR-13324-CS208, Amendment 2 (Rev 2) dated 01 MAR 2019.

This SAP is being written with due consideration of the recommendations outlined in the most recent International Conference on Harmonisation (ICH) E9 Guideline entitled Guidance for Industry: Statistical Principles for Clinical Trials and the most recent ICH E3 Guideline, entitled Guidance for Industry: Structure and Content of Clinical Study Reports.

This SAP describes the data that will be analyzed and the subject characteristics, efficacy, and safety assessments that will be evaluated. This SAP provides details of the specific statistical methods that will be used. The statistical analysis methods presented in this document will supersede the statistical analysis methods described in the clinical protocol. If additional analyses are required to supplement the planned analyses described in this SAP they may be completed and will be identified in the clinical study report (CSR).

2. Study Objectives

In this Phase 2 study, the primary objectives are to evaluate:

- The ocular hypotensive efficacy of netarsudil ophthalmic solutions relative to placebo over a 28-day period
- The ocular and systemic safety of netarsudil ophthalmic solutions relative to placebo over a 28-day period

2.1 Primary Efficacy Endpoint

The primary efficacy endpoint will be the mean of mean diurnal intraocular pressure (IOP) at Week 4 (Day 29).

2.2 Secondary Efficacy Endpoints

The secondary efficacy endpoints include the following:

- Mean of Mean diurnal IOP at Weeks 1 and 2 (Days 8 and 15, respectively)
- Mean change from baseline in mean diurnal IOP at each post-treatment visit
- Mean percent change from baseline in mean diurnal IOP at each post-treatment visit
- Mean IOP at each post-treatment time point
- Mean change from diurnally adjusted baseline IOP at each post-treatment time point
- Mean percent change from diurnally adjusted baseline IOP at each post-treatment time point
- Percentages of subjects achieving pre-specified mean, mean change, and percent mean change in mean diurnal IOP levels

2.3 Safety Endpoints – Treatment Period

The safety endpoints include the following:

- Ocular symptoms/adverse events (AEs)
- Visual Function Questionnaire (VFQ-25) at baseline
- Best Corrected Visual Acuity (BCVA)
- Contrast Sensitivity (CS) testing at baseline
- Objective findings of biomicroscopic examinations (i.e., anterior segment examinations including evaluation of cornea, conjunctiva, lids, and lens)
- Dilated ophthalmoscopy, including vertical cup-disc ratio measurements

Systemic safety assessment will include:

- Vital signs (heart rate and blood pressure)
- Clinical laboratory evaluations (including hematology, clinical chemistry, and urinalysis)
- Pregnancy testing (for women of childbearing potential)

2.4 Safety Endpoints – Observational Period

The endpoints in the observational period include:

- VFQ-25
- BCVA
- CS testing
- Cornea verticillata grading
- Time to cornea verticillata resolution/stabilization

2.5 Statistical Hypotheses

The primary hypotheses are:

- H_{01} : The difference between study eyes treated with netarsudil 0.01% and study eyes treated with placebo (netarsudil 0.01% - placebo), in mean diurnal IOP at Week 4 is equal to 0.
- H_{11} : The difference between study eyes treated with netarsudil 0.01% and study eyes treated with placebo (netarsudil 0.01% - placebo), in mean diurnal IOP at Week 4 is not equal to 0.
- H_{02} : The difference between study eyes treated with netarsudil 0.02% and study eyes treated with placebo (netarsudil 0.02% - placebo), in mean diurnal IOP at Week 4 is equal to 0.
- H_{12} : The difference between study eyes treated with netarsudil 0.02% and study eyes treated with placebo (netarsudil 0.02% - placebo), in mean diurnal IOP at Week 4 is not equal to 0.
- H_{03} : The difference between study eyes treated with netarsudil 0.04% and study eyes treated with placebo (netarsudil 0.04% - placebo), in mean diurnal IOP at Week 4 is equal to 0.

- H_{13} : The difference between study eyes treated with netarsudil 0.04% and study eyes treated with placebo (netarsudil 0.04% - placebo), in mean diurnal IOP at Week 4 is not equal to 0.

Superiority of a netarsudil ophthalmic solution (0.01%, 0.02% and 0.04%) to placebo will be concluded if the two-sided p-value, for testing the difference (netarsudil – placebo) to 0, is < 0.05 , and the point estimate of the difference (netarsudil – placebo) < 0 at Week 4 for that concentration.

3. Study Design and Procedures

3.1 General Study Design

This will be a double-masked, randomized, multicenter, placebo-controlled, parallel-group efficacy and safety trial evaluating reduction of elevated IOP with netarsudil ophthalmic solution over a 28-day treatment period. The purpose of this study is to assess the efficacy and safety of netarsudil ophthalmic solution (0.01%, 0.02%, and 0.04%) compared to placebo in subjects that are 20 years of age or older with open-angle glaucoma (OAG) or ocular hypertension (OHT) in Japan.

All study drugs will be dosed in both eyes (OU) once daily (QD) in the evening. Subjects eligible to be enrolled in this study will be those with a diagnosis of either OAG or OHT. Approximately 208 subjects will be enrolled. Subjects who agree to participate in this study and are enrolled in the study will attend a total of six study visits: Screening Visit, Qualification Visit #1, Qualification Visit #2/Day 1 (baseline), Week 1 (Day 8), Week 2 (Day 15), and Week 4 (Day 29).

Subjects will be required to washout of their pre-study ocular hypotensive medication for a prescribed period (i.e., five days to at least six weeks, depending on the medication) prior to attending Qualification Visit #1. Subjects eligible to be enrolled in this study must meet all inclusion criteria and none of the exclusion criteria at each of the Screening Visit and Qualification Visits #1 and #2. Subjects will receive a baseline eye examination including IOP measurements at the Screening Visit and Qualification Visits #1 and #2, and undergo additional testing at Qualification Visit #2 including VFQ-25, BCVA, and CS testing. If deemed eligible, the subject will be enrolled at Qualification Visit #2 and assigned to placebo or 1 of 3 investigational products (IPs) in a 1:1:1:1 ratio according to a computer-generated randomization list. Randomization will take place using Interactive Web Response Systems (IWRS) methodology and will stratify subjects by site.

Randomized subjects will dose the assigned drug in both eyes QD in the evening (between 20:00 and 22:00 hours) beginning on Day 1 and up to and including the evening prior to the final visit at Visit 6 (Week 4). Procedures conducted at each of the Study Visits 4 to 6 will include safety and efficacy measurements, including IOP assessments. At Visits 4 to 6 (Weeks 1, 2, and 4, respectively), IOP will be assessed at 09:00, 11:00, and 16:00 hours. Following completion of the Visit 6 (Week 4) study visit procedures, subjects will exit the study. For subjects who discontinue early, every possible effort will be

made to assure there is a final visit that includes all examinations listed for Visit 6.0 (Week 4) and dilated ophthalmoscopy.

For subjects who show any evidence of cornea verticillata by slit lamp examination using the grading system for amiodarone keratopathy (Orlando 1984) during the 28-day treatment period, the assigned study drug will be discontinued, all exit visit procedures (Visit 6) will be completed and subject will be followed in an observational period starting as OBS Visit 1 (Day 1) in which subjects will undergo VFQ-25, BCVA testing, CS testing and cornea verticillata grading. All subjects with cornea verticillata will return for monthly surveillance visits (OBS Visit 2, 3 and 4) where they will undergo BCVA testing and cornea verticillata grading for 3 months. If cornea verticillata persists at the 3-month time point (OBS Visit 4), subjects will return every 2 months for BCVA testing and cornea verticillata grading until resolution or stabilization. Resolution is defined as grading of zero of the cornea verticillata grading and stabilization is defined as no worsening of the cornea verticillata grading for a minimum of one year from the commencement of dosing. Once resolution or stabilization is confirmed in both eyes, the subject will undergo VFQ-25, BCVA testing, CS testing and exit the study.

